2.5.2 Laboratory Data

Ionis Pharmaceuticals, Inc. is responsible for the format of the laboratory electronic data transfers and the transfer schedule. Ionis Pharmaceuticals, Inc. is responsible for the review of the clinical laboratory data. Central laboratory data is not stored in the EDC system. Investigator sites have access to the data via lab reports sent directly from the laboratory or through the laboratory's web portal (in which case Investigators only have access to data from their site). To ensure maintenance of the study blind in the ongoing parent study, TTR (also called pre-albumin), RBP4, retinol (also called vitamin A), and NT-proBNP from the first 13 weeks of treatment in this present OLE study is not available to the Sponsor, Investigators, Study Center Personnel, or the patients until the parent study is unblinded.

2.5.3 Pharmacokinetics (PK) Data and Immunogenicity (IM) Data

Ionis Pharmaceuticals, Inc. is responsible for the management and review of the PK and IM data. This process involves reviewing the patient and visit identifiers (i.e., patient demographics) with the clinical data collected in the EDC system. The PK and IM data are not stored in the EDC system. Prior to the parent study unblinding, any ISIS 420915 concentration data sets and IM data sets provided to Ionis Pharmaceuticals, Inc. by the respective bioanalytical labs do not include results for samples collected prior to Week 13, nor do they include results for Unscheduled or early term (ET) samples.

2.5.4 Echocardiogram (ECHO) Data

The ECHO data is collected, analyzed and stored in a secure database by an independent CRO (Cardiac Imaging Core Laboratory and Clinical Trials Endpoints Center at the Brigham and Women's Hospital (CICL)). The sites upload the ECHO data on a secure web-portal for analysis by CICL. ECHO data is firewalled from review by Ionis Pharmaceuticals, Inc until the parent study is unblinded. For the purpose of pre-programming and data cleaning, PAREXEL and a firewalled data manager working at the CRO contracted to perform data management (TRENNIC Data Services) have access to the post-baseline ECHO data.

2.5.5 Electrocardiogram (ECG) Data

All ECG data (machine read) are entered into the Bioclinica EDC by the sites. The Bioclinica data will be used for ECG summary and analysis.

All triplicate ECG waveforms are collected and stored in a secure database by an independent CRO (Applied Clinical Intelligence, LLC (ACI)). Selected ECGs are analyzed by ACI and the resulting data captured in the ACI database as an ECG over-read database. The ECG over-read data are used to support medical monitoring and will not be used for the ECG summary and analysis.

2.5.6 Modified Neuropathy Impairment Score +7 (mNIS+7) and Neuropathy Symptoms and Change Score (NSC)

2.6 Blinding

The Statistical Analysis Plan (SAP) for this OLE study will be finalized prior to the parent study unblinding. An interim analysis specified in section 5 will be performed at the parent study unblinding. At that time, all unblinded information and firewalled datasets in the parent study for this OLE study will be available.

To ensure maintenance of the study blind in the ongoing parent study, TTR, RBP4, retinol, NT-proBNP, PK and Immunogenicity data from the first 13 weeks of treatment in this present OLE study are not made available to the Sponsor, Investigators, Study Center Personnel, or the patients until the parent study is unblinded.

Derived mNIS+7 and the components including NIS, +7 and modified +7, as well as NSC, Norfolk QOL-DN, SF-36, PND, body weight and ECHO information are not made available for sponsor review until the parent study is unblinded. For the purpose of pre-programming and data cleaning, PAREXEL and a firewalled data manager working at the CRO contracted to perform data management (TRENNIC Data Services) have access to the post-baseline mNIS+7, NSC, Norfolk QOL-DN, SF-36, PND, ECHO and body weight. Details are discussed in section 5.2.

3. Analytical Plan

3.1 Statistical Design Summary

This SAP specifies the study endpoints to be analyzed, the study populations, and the methods of analysis. Section 3.2 provides general guidelines to be followed for all analyses, and covers the analysis populations, handling of missing data, and other general topics. Analyses of baseline characteristics are also covered in this section. Section 3.3 discusses the safety analyses. Section 3.4 and 3.5 specifies the efficacy and PD endpoints and methods of analysis for these endpoints. Section 3.6 covers PK analyses.

Section 4 is for the sample size justification. Section 5 presents details on the interim analyses to be conducted for this present OLE study.

The SAP concludes with a references section and appendices.

3.2 General Overview of Analyses

This SAP describes the reporting of data at the EOS for this OLE study (unless specified otherwise). Additionally, some of these data will also be reported for the purposes of the interim analyses.

3.2.1 Analysis Conventions

All reporting will be performed in SAS version 9.3 or higher.

Efficacy results will be summarized under the treatment to which patients were randomized in the parent study. Safety and PK results by treatment group of parent study will be summarized under the treatment to which patients received in the parent study. Should there be any cases after the parent study unblinding in which a patient received treatment other than what was randomized, such cases will be discussed in the OLE study report and noted in footnotes where applicable.

All electronic case report form data, lab data transfers, ECHO, ECG, and mNIS+7 score data, as well as any outcomes derived from the data, will be provided in the patient data listings. Patient data listings will be presented for all patients enrolled into the OLE study, will include all data collected during the OLE phase, and will be sorted by treatment group of parent study, patient ID, visit, and time point (where appropriate).

Central laboratory assessments will be included in the summary tables; local laboratory assessments will only be included in listings. Exceptions to the use of local laboratory assessment in summary tables are made for platelets, where summary tables will use both local and central laboratory results.

[figure not shown]
All tables will present the population frequencies in each treatment group in the parent study and/or subgroup (where appropriate) and will indicate the number of patients with non-missing data and the denominators for percentages.

Descriptive summary statistics including n, mean, percentiles (e.g., median, 25th percentile [P25], and 75th percentile [P75]), standard deviation, and range (minimum, maximum) for continuous variables, and counts and percentages for categorical variables, will be used to summarize data by treatment group of the parent study. Summaries of PK parameters, if applicable, will also present geometric mean, standard deviation of log-transformed data, and coefficient of variation, expressed as a percent (%CV). Where appropriate, p-values will be reported. All statistical tests will be conducted using 2-sided tests with a 5% Type I error rate, unless otherwise specified.

Age will be presented in years. Weight will be presented in kg. Height will be presented in cm. Temperature will be presented in °C. Laboratory values will be summarized using standard units (SI units). Precision for displays will use the following conventions. Means, percentiles (e.g., median, P25, and P75), least squares means, difference in least squares means will be displayed to one more decimal place than measured values. Standard deviations and standard errors will be displayed to

two more decimal places than measured values. The minimum, maximum and confidence intervals (CI) will be displayed using the same number of decimal places as the recorded values. All raw values presented in listings will be displayed to the measured precision. Percentages will be displayed to one decimal place. P-values will be displayed to 3 decimal places. CI will be presented using a comma separator rather than a dash.

As shown in the schematic below, boxplots will display values from minimum to maximum within the upper and lower fences, the likely range of variation from P25 to P75 and the median. A symbol inside the box will indicate the mean. A segment inside the box will show the median and "whiskers" above and below the box will show the locations of the minimum and maximum observations within the upper and lower fences (see definition below). Individual observations outside the upper or lower fences will also be marked.

All efficacy and PD endpoints, except GLS will be assessed on the Full Analysis Set (FAS) and Per-Protocol Set (PPS). Refer to Section 3.2.2 for a description of the patient populations. Safety analysis will be performed on the Safety Set (SS) or Longitudinal Safety Set (LSS). PK endpoints will be assessed in the Pharmacokinetic Set (PKS) as applicable. ECHO endpoints including GLS will be assessed for all enrolled subjects, the ECHO subgroups and in the Cardiomyopathy-ECHO (CM-ECHO) Set.

An interim analysis of this OLE study will take place at the same time when the parent study database is locked and unblinded at EOT. Other interim analyses may be performed with the timing of the analyses coinciding with regulatory requirements or study milestones. See section 5 for details on the interim analyses. The final EOS analyses will take place after all patients have completed the study and the database has been locked.

3.2.1.1 Definitions and Computational Formulas

3.2.1.1.1 Day 1 of ISIS 420915 and CS3 Study Day 1:

- Day 1 of ISIS 420915 will refer to the first day ISIS 420915 is administered to the patient. For patients on active treatment in the parent study, Day 1 of ISIS 420915 will be the first day ISIS 420915 is administered in the parent study. For patients on placebo in the parent study, Day 1 of ISIS 420915 will be the first day ISIS 420915 is administered in this OLE study.
- **CS3 Study Day 1** will refer to the first day ISIS 420915 is administered to the patient in this OLE study.
- **CS2 Study Day 1** will refer to the first day study drug (ISIS 420915 or Placebo) is administered to the patient in the parent study.

3.2.1.1.2 Three baselines are defined as following:

- Parent study baseline will be the baseline of the parent study, which is defined for most endpoints, unless specified, as the last non-missing value prior to the Day 1 of treatment, ISIS 420915 or Placebo, in the parent study. Considerations for mNIS+7, ECG, NSC, ERG and laboratory assessment are detailed below.
 - o For mNIS+7 and its individual components, the **parent study baseline** will be defined as the average of two assessments taken within 60 days prior to the first dose of Study Drug. If only one assessment has been done, the single assessment will be used in place of the average. Rarely, for patient convenience, the **parent study baseline** mNIS+7 assessment(s) (or a subset of this assessment) will have been completed early in the parent study treatment period rather than pre-treatment. These assessments will be included in the analysis as valid baseline assessments provided they are taken within one week after the first dose. The rationale for this is that the pharmacology of the drug indicates that the drug will have no effect on mNIS+7 this early in treatment, and including these values as the baseline assessments will allow these patient's data to be included in the efficacy analysis. Further details of the assessment level data imputation are described in Section 3.2.1.3 of this document. Note that the NIS screening assessment can be used as one of the two assessments provided it was done within 60 days of first dose of Study Drug. Further details on how to handle missing baseline results are described in section 3.2.1.3.
 - o For NSC and individual components, the parent study baseline will be defined as the average of two assessments taken within 60 days prior to the first dose of Study Drug in the parent study. If only one assessment has been done, the single assessment will be used in place of the average. Because NSC score is collected during the NIS assessment procedure in the parent study, it is possible it could be completed early in the treatment period rather than pre-treatment. These assessments will be included in the analysis as valid parent study baseline assessments provided they are taken within one week after the first dose of the parent study.
 - For ECG, the parent study baseline will be defined as the average of the triplicate taken on Day
 1 Pre-dose in the parent study. If only one or two assessments are available, the single

- assessment or average of the two assessments will be used. In the case that Day 1 Pre-dose is missing, screening visit results of the parent study will be used as baseline.
- The protocol permitted baseline ERG and ophthalmology examinations can be done up to one
 week after CS2 Study Day 1. Assessments done within one week of first dose will be included in
 the analysis as valid parent study baseline assessments.
- The **parent study baseline** laboratory assessment including PD will be defined as the average of all non-missing pre-dose assessments in the parent study.
- OLE study baseline will be defined as the last non-missing assessment prior to the first dose of ISIS 420915 in the OLE study (CS3 Study Day 1). However the last assessment must be collected within 3 months (90 days) before CS3 Study Day 1 of OLE study in order to be used to derive the baseline, i.e. if there is no assessment within 3 months, the OLE study baseline will be missing. Depending on when the assessments are scheduled to be collected this may be derived from the CS3 Study Day 1 or the screening visit in the OLE study or the last non-missing assessment from the parent study. Considerations for mNIS+7, NSC, and ECG are detailed below:
 - For mNIS+7 (and its individual components) and NSC (and its individual components), if the last assessment is the Week 66 assessment in CS2, the average of the two Week 66 assessments will be taken (as defined in the CS2 Statistical analysis plan). If only one assessment has been done, the single assessment will be used.
 - o For ECG, the OLE study baseline will be defined as the average of the triplicate taken at the screening visit of the OLE study. If only one or two assessments are available, the single assessment or average of the two assessments will be used. If ECG wasn't measured at the screening visit of the OLE study, the last visit in the parent study collected within 3 months (90 days) before CS3 Study Day 1 of OLE study will be used as baseline.
- ISIS 420915 baseline will be the parent study baseline for patients randomized to ISIS 420915 in the parent study, and will be the **OLE study baseline** for patients randomized to placebo in the parent study.

3.2.1.1.3 Three baselines for analyses:

- Efficacy analyses and PD analyses are based on the parent study baseline and the OLE study baseline. Details of separate analyses based on each baseline will be specified in the section 3.4 and 3.5.
- Safety analyses are based on **ISIS 420915 baseline**. Details of separate analyses based on each baseline will be specified in the section 3.3.
- Further details of which assessments will be considered baseline for ECHO analyses for this present OLE study are included in a separate SAP for the ECHO data.
 - 3.2.1.1.4 On-treatment, post-treatment and on-study in either the parent study or the OLE study (Details on the planned summary/analysis at each period are discussed in the section 3.2.1.4):

- For efficacy endpoints except for BMI and mBMI:
 - The efficacy on-treatment period for the parent study spans the time during which the study treatment is administered from the **CS2 Study Day 1** until 52 days after the last dose of medication in the parent study. The efficacy on-treatment period for the OLE study is from the **CS3 Study Day 1** until 52 days after the last dose of medication in the OLE study
 - For both studies the efficacy post-treatment period starts on the day after the efficacy treatment period and ends on the day of the patient's last contact datewithin the study.

• For BMI, mBMI and PD endpoints:

- The on-treatment period for the parent study spans the time during which the study treatment is administered from the CS2 Study Day 1 until 28 days after the last dose of medication in the parent study. The on-treatment period for the OLE study is from the CS3 Study Day 1 until 28 days after the last dose of medication in the OLE study.
- o For both studies the post-treatment period starts on the day after the treatment period and ends on the day of the patient's last contact date within the study.

• For safety endpoints except for ERG:

- The on-treatment period for the parent study spans the time during which the study treatment is administered from the CS2 Study Day 1 until 7 days after the last dose of medication in the parent study. The on-treatment period for the OLE study is from the CS3 Study Day 1 until 7 days after the last dose of medication in the OLE study.
- For both studies the safety post-treatment period starts on the day after the safety treatment period and ends on the day of the patient's last contact date within the study.
- For both studies the Safety on-study period spans the time drug is first administered until the day of the patient's last contact date within the study.
- The period for the longitudinal safety analysis spans the time from the first dose of ISIS
 420915 in the parent study and ends on the day of the patient's last contact date within the study. The subject's last contact date is defined as follows:
 - (1) for subjects who signed an informed consent form in the OLE study, it is the last contact date within the OLE study;
 - (2) for subjects who did not sign an informed consent form in the OLE study but had been administered ISIS 420915 in the parent study, it is the last contact date within the parent study. The details of longitudinal safety analysis for AEs and safety lab results will be addressed in section 3.3.

For ERG:

The on-treatment period for the parent study spans the time during which the study treatment is administered from the CS2 Study Day 1 until 28 days after the last dose of medication in the parent study. The on-treatment period for the OLE study is from the CS3 Study Day 1 until 28 days after the last dose of medication in the OLE study.

- For both studies the safety post-treatment period starts on the day after the safety treatment period and ends on the day of the patient's last contact date within the study.
- The PK on-study period for the OLE study spans the time ISIS420915 is administered in the OLE study (CS3 Study Day 1) until the day of the patient's last contact date within the OLE study.
- The Immunogenicity (IM) on-study period for the OLE study spans the time the first dose of ISIS420915 in the parent study and ends on the day of the patient's last contact date within the OLE study. This period is for defining patient IM status (Details in section 3.2.1.1.6).

3.2.1.1.5 Durations of study drug exposure and total dose of ISIS 420915:

Durations of overall drug exposure (days) across both studies will be derived as the difference in
days between the date of the last dose of ISIS 420915 and Day 1 of ISIS 420915 plus one. For
patients who are not enrolled in the OLE study, the last dose of ISIS 420915 is administered in the
parent study; for patients who are enrolled in the OLE study, the last dose of ISIS 420915 is
administered in the OLE study.

The total dose of study drug during the treatment period for either the parent study or the OLE study will be computed for patients receiving ISIS 420915 by summing the dose administered between **Day 1 of ISIS 420915** and the last dose date in the parent study for patients who are not enrolled in the OLE study or the last dose date in the OLE study for patients who are enrolled in the OLE study. Total dose will be summarized in milligrams as part of longitudinal safety analysis.

• Duration of drug exposure in OLE study (days) will be derived as the difference in days between the date of the last dose of ISIS 420915 in OLE study and **CS3 Study Day 1** plus one.

The total dose of study drug during the treatment period for the OLE study will be computed for patients receiving ISIS 420915 in the OLE study by summing the dose assigned between **CS3 Study Day 1** and the EOT date or date of early termination in OLE study. Total dose will be summarized in milligrams.

3.2.1.1.6 *Immunogenicity (IM):*

- For subjects with negative IM status in the parent study, the onset (T_{first}) of anti-ISIS 420915
 antibodies in OLE study will be derived as difference in days between the date when first
 immunogenicity sample becomes confirmed positive (i.e., positive sample IM status) in OLE study
 and Day 1 of ISIS 420915 plus one.
- For subjects with positive IM status in the parent study, the onset (T_{first}) of anti-ISIS 420915 antibodies in the parent study will be used as the onset of the OLE study.

3.2.1.1.7 BMI and mBMI:

• Body mass index (BMI) will be computed using the formula:

BMI = (weight in kilograms) / [height in cm / 100]²

Modified BMI (mBMI) will be computed from BMI and serum albumin levels by:

mBMI = BMI * serum albumin (g/L).

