6.1.1 Screening Assessment Period

Before any study-specific procedures or evaluations are initiated, patients must sign and date the informed consent form. A maximum period of 4 weeks is allowed between a patient's last dose in ISIS 420915-CS2 (CS2 Week 65 visit) and initiation of dosing in this study (CS3 Day 1 visit). Periods longer than 4 weeks may be considered after discussion and approval by the Study Medical Monitor. All screening assessments must be completed during this period. An exception is the 24-hour urine collection (which includes a serum creatinine blood draw) that may be done at any time during the screening period or during Week 1 on treatment. Safety clinical laboratory parameters and assessments from ISIS 420915-CS2 may be used for screening evaluation if they were obtained within 4 weeks of Study Day 1. A longer period may be considered after discussion and approval from the Study Medical Monitor.

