Appendix A Schedule of Procedures Continued

	Screen							Υ	ear 1							Ye	ar 2			Y	ear3	
	1	W	W	W	W	W	W	W	W	W	W	W	W	W	W	W	W	W	W	W	W	W
Study Week	:S 4 weeks [⊥]	1	4	7	10	13	15	18	21	23	26	29	39	52	65	78	91	104	117	130	143	156
		D	D	D	D	D	D	D	D	D	D	D	D	D	D	D	D	D	D	D	D	D
Study Day	S-28 to S-1	1	22	43	64	85	99	120	141	155	176	197	267	358	449	540	631	722	813	904	995	1086
Visit Window(+/- Days)		0	7	7	7	7	7	7	7	7	7	7	7	7	10	10	10	10	10	10	10	10
Labs																						
Pregnancy Test ⁷ ·A	х3	X		X		X					X			X		X	XS	X	XS	X	XS	X
Chemistry PanelA(fasting)	хЗ	X	XS	X	XS	X	XS	XS	XS	XS	X	XS	XS	X	XS	X	XS	X	XS	X	XS	X
Additional Platele 1 ta 3 nd Serum Creatinine		x3 X XS X XS XS XS XS XS XS X X X X X X X X X X X X X																				
HematologI	хЗ	X	XS	X	XS	X	x8	XS	XS	XS	X	XS	XS	X	XS	X	XS	X	XS	X	XS	X
UrinalysisA	х3	X	XS	X	XS	X	x8	XS	XS	XS	X	XS	XS	X	XS	X	XS	X	XS	X	XS	X
24 hour Urine (serum creatinine required) ⁹	X																					
Thyroid PanelA	х3			X		X					X			X		X		X				X
PT, aPTT, INRA	х3			X		X					X			X		X		X				X
RetinolA(fasting)		X		X		X					X			X		X		X		X		X
hs-cRpA		X		X		X					X			X		X	XS	X	XS	X	XS	X
PD PanelA(fasting)		X		X		X		XS	XS		X		XS	X	XS	X	XS	X	XS	X	XS	X
NT-proBNPA		X		X		X		XS			X		XS	X	XS	X	XS	X	XS	X	XS	X
Immunogeniciif				X		X		XS			X		XS	X	XS	X	XS	X	XS	X	XS	X
PK TroughA		X		X		X		XS			X		XS	X	XS	X	XS	X	XS	X	XS	X

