Appendix A Schedule of Procedures Continued

Shaded columns represent non-clinic visits. Labs as indicated may be collected by the Sponsor's home healthcare service or by a local laboratory (with prior Sponsor approval). Patients also have the option to go to clinic for these visits.

Note: If not specifically labeled, "X" means anytime

- 1 For an individual patient, a maximum period of 4 weeks is allowed between a patient's last dose in ISIS 420915-CS2 (CS2 Week 65 visit) and initiation of dosing in this study (CS3 Day 1 visit). All screening assessments must be completed during this period. Longer periods may be considered after discussion and approval from the Study Medical Monitor
- 2 ISIS 420915 can be administered in the clinic or at home by the patient/caregiver. It is not necessary for ISIS 420915 to be administered on site during clinic visits. Clinic visits should occur on a dosing day, 7 days after the previous dose
- 3 Assessments from ISIS 420915-CS2 may be used for screening evaluation if they were obtained within 4 weeks of Study Day 1. A longer period may be considered after discussion and approval from the Study Medical Monitor
- 4 Blood pressure should be taken after the patient has been sitting for ≥ 5 min
- 5 A +/- 2-week window is given for ERG and ophthalmology examinations. The early termination ERG and ophthalmology examinations are only done if the patient discontinues treatment after ≥ 9 mo of dosing or unless deemed necessary by Investigator or Study Medical Monitor
- 6 To collect AEs, conmeds, and the general wellbeing of the patient
- 7 For females of childbearing potential only, by serum βhCG except on Day 1 by urine hCG (pre-dose)
- 8 To be collected by either a local laboratory (if approved by Sponsor), Sponsor appointed home healthcare service, or Study Center as arranged by the Study Center personnel
- 9 The 24-hour urine collection can be done any time during the screening period or during Week 1 on treatment. Serum creatinine blood draw required
- 10 If ISIS 420915 administration, ERG, or ophthalmology examinations are to be performed on the same day as a mNIS+7 assessment, they should be performed after the mNIS+7 assessment is complete. For the Week 78 and Week 156 visits, 2 mNIS+7 assessments will be performed on separate days. A maximum of 2 weeks from the visit (Week 78 or Week 156) will be allowed to complete both assessments
- 11 Norfolk QOL-DN should be the first assessment performed at the visit

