9.2 Additional Analyses added for Final Analyses

9.2.1 Based on OLE data only

- Summary of disposition and protocol deviation associated with COVID-19 based on CS3
 Enrolled Patients
- Summary of ISIS 420915 Trough Plasma Concentrations (On-Study) based on safety set.
- Summary of Complement Results (Complement C3, Complement C4, Complement Split Bb, Complement Split C5a) by visit based on safety set
- Summary of TEAE by System Organ Class and Preferred Term and by PND score (On-Study)
 based on safety set
- Lab shift table for Hematology (Hemoglobin, Lymphocyte, Neutrophil, White Blood Cell), Chemistry Test, Coagulation Test, Urinalysis test, Urinalysis Results from Central Lab Based on 24-hr Urine Collections, Confirmed Peak ALT, Confirmed Peak AST, Confirmed Peak Total Bilirubin (On-study) based on safety set.
- Incidence of Post-baseline abnormality, including lab Complement Results, vital signs and body weight and QTcF.

Efficacacy endpoints

On-treatment: Add Statistical Analysis of Change from CS2 Baseline to efficacy endpoints:

mNIS+7, NIS+7, NIS, Modified +7, +7, NSC composite and component score, mNIS+7 composite score, Norfolk QOL-DN, NSC total and domain score and selected questions, SF-36 component and Domain Scores. Norfolk QOL-DN Symptoms Domain Score based on Stage 1 Patients, Norfolk QOL-DN Physical Functioning/Large Fiber Neuropathy Domain Score based on Stage 2 Patients

Post-treatment:

Show Descriptive statistics of absolute value, change from baseline and percent change from baseline in mNIS+7, NIS+7, NIS, Modified +7, +7 Composite and Component, Norfolk QOL-DN Total and Domain Scores, SF-36 Scores, NSC score and Select Questions from NSC

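### The one scheduled 24-hour urine may be collected after the first dose, but the SAP has no baseline rule for it, so some former-placebo patients may lack a baseline in the 24-hour urine shift table

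*Combined protocol and SAP*

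**What the plan says.** **Timing of the collection.** Protocol 6.1.1 exempts the 24-hour urine from the rule that screening assessments are finished before dosing: it "may be done at any time during the screening period or during Week 1 on treatment". Footnote 9 of Appendix A repeats this: "The 24-hour urine collection can be done any time during the screening period or during Week 1 on treatment".

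**How often it is scheduled.** In Appendix A, the row "24 hour Urine (serum creatinine required)" has one mark, in the screening column. It has none for the rest of Years 1 to 3, Years 4 and 5, early termination or post-treatment. Any later collection follows a renal monitoring or stopping trigger (protocol 8.5.2 and 8.6.2).

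**Baseline.** SAP 3.2.1.1.2 states that the "OLE study baseline will be defined as the last non-missing assessment prior to the first dose of" study drug in the OLE. The value must fall within 90 days before CS3 Study Day 1, otherwise the baseline is missing; a parent-study value inside that window may serve. Safety analyses use the ISIS 420915 baseline (SAP 3.2.1.1.3). On that baseline the SAP says "ISIS 420915 baseline will be the parent study baseline for patients randomized to ISIS 420915" in CS2; for those randomized to placebo it is the OLE study baseline.

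**Output.** SAP 9.2.1 adds on-study laboratory shift tables for the final analysis, including "Urinalysis Results from Central Lab Based on 24-hr Urine Collections".

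**Allowance for other measures.** For the parent-study ERG and ophthalmology baselines, which the protocol let sites do shortly after dosing, SAP 3.2.1.1.2 says: "Assessments done within one week of first dose will be included in" the analysis as valid baselines. Parent-study mNIS+7 and NSC have a similar one-week allowance. The special cases listed under the OLE baseline are mNIS+7, NSC and ECG only.

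**The concern.** The protocol treats a Week 1 collection as a legitimate way to do the screening 24-hour urine. The SAP's general rule treats the same sample, if taken after the first dose, as post-baseline data. Nothing reconciles the two for this test, although the SAP does so for other measures where the protocol gave similar latitude.

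This matters mainly for former-placebo patients. They start the drug in CS3, so a before-and-after comparison of 24-hour protein is informative in them, and renal impairment is an adverse event of special interest (SAP 3.3.2.1). No other scheduled CS3 collection can replace the missing baseline. If a renal trigger later leads to a 24-hour urine, that result may have nothing to be compared with in the shift table. The parent-study baseline used for former-active patients does not depend on when the CS3 sample was taken.

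**Working it through.** The plan states no figure to reproduce. The check compares the texts, then does some date and count arithmetic.

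**Classification of a Week 1 sample taken after the first CS3 dose, former-placebo patient**

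| Question | Source | Answer |
|---|---|---|
| Does the protocol allow it? | Protocol 6.1.1; Appendix A footnote 9 | Yes |
| Is another 24-hour urine scheduled in CS3? | Appendix A | No |
| Can it be the OLE baseline? | SAP 3.2.1.1.2 | No, it is not before the first dose |
| Is there an exception for it? | SAP 3.2.1.1.2 | No |
| In which period does it fall? | SAP 3.2.1.1.4 and 3.2.1.4 | On-study, which starts at first dosing |
| Can another value be the baseline? | SAP 3.2.1.1.2 | Only a pre-dose value within 90 days, which here means one from CS2 |

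**Which CS2 samples could serve.** CS2 Week 65 has target Day 449 (SAP Appendix 3, Table 1). The gap from the last CS2 dose to CS3 Day 1 is ideally 1 week and normally at most 4 weeks (protocol 3.4.1).

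- 7-day gap: CS3 Day 1 = CS2 Day 449 + 7 = 456; earliest eligible day = 456 − 90 = 366.
- 28-day gap: CS3 Day 1 = CS2 Day 449 + 28 = 477; earliest eligible day = 477 − 90 = 387.

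A CS2 24-hour urine from about Day 366 to 387 onward would therefore still be a valid OLE baseline. The documents do not say whether CS2 collected one then. The 24-hour urine row does not carry footnote 3, which marks CS2 assessments usable for screening, but that omission does not limit the SAP's own fallback.

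**How many could lack a baseline.** SAP 1.1 plans 90 active and 45 placebo patients in CS2, so former-placebo enrolment is at most about 45 (45/135 = 33%). Let u be the share sampled in Week 1 after dosing and f the share of those with an eligible CS2 value. Both are assumptions. Number without baseline = 45 × u × (1 − f).

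| u | f = 0 | f = 0.5 | f = 1 |
|---|---|---|---|
| 10% | 4.5 | 2.2 | 0 |
| 25% | 11.2 | 5.6 | 0 |
| 50% | 22.5 | 11.2 | 0 |
| 100% | 45 | 22.5 | 0 |

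**How many lose a meaningful shift.** This also needs a later triggered collection, with probability t, also unstated. As an illustration with f = 0: u = 20% and t = 10% gives 45 × 0.20 × 0.10 = 0.9; u = 50% and t = 25% gives 45 × 0.50 × 0.25 = 5.6. On those assumptions the loss is about 1 to 6 patients, before any CS2 fallback.

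**The case against.** The strongest reply is that renal safety does not rest on this table. Urinalysis and chemistry are scheduled pre-dose on Day 1 (Appendix A). They include the protein/creatinine and albumin/creatinine ratios, serum creatinine and CKD-EPI clearance (Appendix B), and SAP 3.3.4.3 tabulates all four. The renal event of special interest is defined by a MedDRA query, not by 24-hour urine, and all laboratory results are listed (SAP 3.3.4). The study has no formal hypotheses (SAP 1.3). This stands, and it confines the effect to one descriptive table.

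A second reply is that a strict pre-dose safety baseline is defensible. The SAP's one-week allowances all concern parent-study baselines, and the pharmacological reason it gives, no drug effect that early, is stated for mNIS+7 only. This stands in part. The ERG and ophthalmology allowance covers safety measures and rests on protocol permission, which is the situation here; but no argument is offered that urine protein cannot change within a week of the first dose.

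A third reply is that the texts do not settle how the table works. SAP 9.2.1 does not name its baseline, so the ISIS 420915 baseline is inferred from the general safety rule. The missing-baseline rule in SAP 3.2.1.3 concerns change from baseline; it does not say whether a shift table drops such patients or shows them as missing. Both points are fair. Either way, no shift can be classified for them.

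**Conclusion.** The mismatch is real and minor. A former-placebo patient has no baseline for the 24-hour urine shift table if the Week 1 option was used after dosing and no CS2 24-hour urine lies in the 90 days before CS3 Day 1. The sample meant as the screening value is then counted as post-baseline. The number is between 0 and about 45 planned patients and cannot be narrowed without knowing uptake of the option and what CS2 collected. Only those with a later event-driven collection lose a meaningful comparison.

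Three stronger readings are tempting and are not supported:

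- **Every former-placebo patient who uses the option loses the baseline.** The bullet that sets the pre-dose rule also admits a parent-study value within 90 days.
- **An assumed uptake of 20% to 50% means that 9 to 22 patients are harmed** (45 × 0.20 = 9; 45 × 0.50 = 22.5). That counts possible missing baselines, ignores the CS2 fallback, and includes patients with no later collection to compare.
- **Pre-existing proteinuria would appear as a shift arising on drug because the baseline is missing.** With a missing baseline, the table cannot show a shift from normal to abnormal.

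The conclusion assumes that the table uses the ISIS 420915 baseline.

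**What to change.** Add one bullet under the OLE study baseline in SAP 3.2.1.1.2, on the model of the ERG and ophthalmology rule. When no pre-dose 24-hour urine exists within 90 days before CS3 Study Day 1, the protocol-permitted collection done within one week after CS3 Study Day 1 is the OLE baseline for the 24-hour urine parameters, and it is excluded from post-baseline values. Name the baseline used for this shift table in SAP 9.2.1, and footnote the number of baselines taken after dosing.

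The cost is a few lines of SAP text and one footnote; no patient procedure changes. The downside is that a few baselines would follow one dose and could absorb a very early drug effect, which the footnote makes visible.
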